### **2.2. Secondary Objectives**

The secondary objectives of this study are:

[figure not shown]
- To evaluate the effect of ManNAc on disease-relevant biomarkers;
- To measure the effect of ManNAc on clinical aspects of GNE myopathy and identify clinical endpoints suitable for subsequent clinical trials.

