### 3.3.1.1. Determining Treatment Effect using the Progression Model GNE Myopathy

The disease progression model can be used to determine whether an intervention changes the rate of disease progression compared to the natural progression under no intervention. The rate of decay for each muscle (at any given disease age) is estimated in the model. To determine whether a therapy affects disease progression, the model incorporates a treatment effect parameter (referred to as  $\gamma$ ) that determines whether the intervention slows the rate of decline compared to no intervention. If  $\gamma$  is equal to 1 there is no treatment effect (as the rate of progression is the same with intervention than with no intervention). If  $\gamma$  is less than 1, an intervention slows the rate of progression as compared to no intervention. If  $\gamma = 0.5$ , the treatment slows the rate of muscle progression by 50%. If  $\gamma$  equals zero, the treatment has stopped the rate of progression (Figure 3).

We have determined that using muscle strength as measured by QMA as a primary endpoint and the progression model as primary analysis, significantly increases power and reduces the number of subjects required to determine treatment effect in clinical trials when compared to other tested endpoints. To inform the design of the clinical trial to determine efficacy of a potential therapy for GNE myopathy, utilizing the primary efficacy endpoint and analysis described above, simulations of the design under multiple scenarios were performed. Scenarios included different treatment effects ( $\gamma$ ), number of patients, duration of treatment, randomization and frequency of visits. For each scenario 1,000 trials were simulated. It was determined that a trial enrolling 50 subjects, a 3:1 randomization (treatment:placebo),

duration of 2 years and follow-up visits every 6 months would have the following conditional probabilities of trial success: if the treatment slows the rate of decline by  $\geq 50\%$  ( $\gamma \geq 0.5$ ), 25% ( $\gamma = 0.25$ ) and 0% ( $\gamma = 0$ ), the probabilities of trial success would be  $\sim 98.8\%$ , 75.5% and  $< 1\%$ , respectively. Therefore, the probabilities of trial success are conditional of an assumed effect size. By extending the current study, we will gain understanding of the magnitude of effect size of ManNAc, giving us important information to refine the design of our upcoming pivotal clinical trial.

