#### **4.11. Randomization and Blinding**

There will be no blinding or randomization.

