### 5.2.1.4. Other Rehabilitation Medicine Assessments

Other assessments may be performed at baseline and follow-up visits and will include muscle strength using the 10-point manual muscle testing (MMT-28) scale, Adult Myopathy Assessment Tool (AMAT), 6-min walk test (may be replaced by 10-meter walk test), timed up-and-go test, forward/functional reach test. The Jebsen Standardized Hand Function test will be done at baseline, 365 days (12 months) and 730 days (24 months).

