## 6. DESCRIPTION OF STUDY POPULATION

### 6.1. Estimated Number of Participants

This study will enroll 12 subjects with GNE myopathy divided into two dosing cohorts (cohort size = 6) assigned to receive ManNAc at either 3,000 mg BID or 6,000 mg BID for a 7-day pharmacokinetics study, for a total of 6,000 mg or 12,000 mg per day, respectively. All patients receive 6,000 mg BID for the remainder of the study beyond 7 days. Accrual ceiling will be set at 30 subjects to allow for subject replacement if needed. We anticipate enrollment of the 12 subjects within 1 year.

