#### 7.1.1. General Reporting Conventions

Standard descriptive statistics will include the number (n), mean and standard deviation (SD), median, minimum, and maximum values for continuous variables. For categorical variables, the frequency of subjects will be provided along with the percentage based on the number of subjects with available data. Unless otherwise indicated, summaries will be based on observed data (i.e., no missing data will be imputed).

Any statistical testing and/or provided confidence intervals (CI) are provided as an aid in interpreting study results and are not intended as claims. Results from this study may be used in designing future studies.

Summaries will be provided by treatment group for the individual ManNAc treatment groups (6,000 mg and 12,000 mg), a combined ManNAc group and the combined control subjects from all two cohorts.

Analyses will be generated using SAS® version 9.2 or higher. Analysis on QMA will be performed using R®.

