#### **7.2.5. Lectin Staining on Muscle Biopsies**

The fluorescence will be quantified in 5 different images per slide with  $\geq$  muscle cells per field and analyzed as a change from baseline to 90 days using a paired t-test.

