#### **7.2.7. Other Rehabilitation Medicine Evaluations**

Changes in clinical measurements will be analyzed as a change from baseline to last visit using a paired t-test or Wilcoxon rank sum test based on parametric quality of the data.

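### Section 7.2.7 names the Wilcoxon rank sum test, a two-independent-sample test, as the non-parametric option for a within-subject change; the paired counterpart is the signed-rank test

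*Combined protocol and SAP*

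**What the plan says.** Section 7.2.7 of the combined protocol and SAP covers the clinical measurements other than QMA. They are to be analysed as a "change from baseline to last visit using a paired t-test or Wilcoxon rank sum test based on parametric quality of the data". Two tests are offered for one quantity, and the shape of the data decides between them.

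Section 5.2.1.4 lists the measures. They include "muscle strength using the 10-point manual muscle testing (MMT-28) scale", the AMAT, walking, timed up-and-go and reach tests, and the Jebsen hand test. Each is taken in the same subjects at baseline and again later.

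Other sections bear on whether a second group exists:

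- Section 4.11: "There will be no blinding or randomization".
- Section 6.1: "All patients receive 6,000 mg BID for the remainder of the study beyond 7 days".
- Appendix A gives the reference therapy as none.
- Section 7.1.1 plans summaries by ManNAc dose group and for a combined set of control subjects.

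Section 7.2.5 handles a similar before-and-after comparison, lectin staining, which is "analyzed as a change from baseline to 90 days using a paired t-test". No non-parametric option is named there. The signed-rank test is not mentioned anywhere in the document.

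**The concern.** The rank sum (Mann-Whitney) test asks whether two independent samples come from the same distribution. The question in 7.2.7 is whether the same people changed. The non-parametric test that goes with a paired t-test is the signed-rank test, which works on each subject's own difference.

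The fallback could well be used. The planned sample is 12. Section 5.2.1.4 lists scored scales and timed tests, for which a normal distribution cannot be taken for granted. An analyst who judged a measure non-normal and followed the text would reach for a test that does not fit the data structure.

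At stake is how the other clinical measures are read. A secondary objective in Section 2.2 is to "identify clinical endpoints suitable for subsequent clinical trials", and a p-value that ignores pairing says little about within-subject change in a candidate endpoint.

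**Working it through.** **Is there a stated figure to reproduce?** No. The plan gives no power, effect size, SD or within-subject correlation for this analysis. The check is one of reading, followed by an illustration on assumed data.

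**Step 1: can the named test be applied to the named quantity?** A change from baseline gives one number per subject, hence one sample of at most 12 values. A rank sum test needs two samples, so taken literally it cannot be run without either finding a second group or abandoning the change score.

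**Step 2: is there a second group?** Section 7.2.7 names none. The dose groups in Section 7.1.1 are the only candidates within the study. They differ by plan only in the first 7 days, after which Section 6.1 puts everyone on one dose. The control subjects in Section 7.1.1 have no counterpart in a design with no randomization and no reference therapy, and 7.2.7 does not refer to them. A between-cohort comparison would also answer a different question from the paired t-test offered in the same sentence.

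**Step 3: what if baseline and last visit were entered as two groups?** This departs from 7.2.7's own change-score wording, but it is the one way to make the rank sum test run on these data.

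Worked case (assumed data): baselines are 0, 1, ..., n−1, and every subject declines by 1.5 units plus a tiny amount to break ties. The sizes are n = 12 (planned) and n = 8 (the number Section 3.8.2.2 reports as still on 6 g twice daily). The SD of the baselines is √(n(n+1)/12).

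| | n = 12 | n = 8 |
|---|---|---|
| Baseline SD | √(12×13/12) = 3.61 | √(8×9/12) = 2.45 |
| Decline in SDs | 1.5/3.61 = 0.42 | 1.5/2.45 = 0.61 |
| Signed-rank, exact two-sided p (all differences one way) | 2/2¹² = 0.0005 | 2/2⁸ = 0.008 |
| Rank sum U, of n² pairs | 89 of 144 | 43 of 64 |
| U expected under no change | 72 | 32 |
| Rank sum, exact two-sided p | 0.35 | 0.28 |

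U counts the baseline/follow-up pairs in which the baseline is higher. Baseline i exceeds follow-up j when j ≤ i+1. For n = 12 that gives (2+3+...+12)+12 = 77+12 = 89. For n = 8 it gives (2+...+8)+8 = 35+8 = 43.

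Every subject got worse. The signed-rank test sees this, and the rank sum test loses it in the spread between subjects.

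**Step 4: does the misuse create false positives?** Simulated normal pairs with no true change, n = 12, two-sided 0.05, 4,000 trials per setting, gave these rejection rates:

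| Assumed correlation | Signed-rank | Rank sum |
|---|---|---|
| 0.5 | 3.8% | 0.7% |
| 0.8 | 3.9% | 0.1% |
| 0.9 | 4.7% | 0.0% |

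At correlation 0, a separate simulation (20,000 trials) gave 4.6% for the rank sum test. The rate stays below the nominal 5% throughout, and the test becomes more conservative as the correlation rises. At correlation 0 there is no pairing to lose and the two tests perform about alike.

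**The case against.** The strongest reply is that nobody would make this mistake. The sentence describes a change score and puts the test next to a paired t-test, and Section 7.2.5 uses a paired t-test for the same kind of comparison. A competent analyst would read the phrase as a slip for signed-rank. Most of that stands: a naming slip is the likeliest explanation, and Step 3 shows what a misreading would do, not what 7.2.7 instructs. It does not make the text right. Section 7.5 requires any departure from the plan to be described in the study report, so using the correct test would formally count as one.

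A second reply is that the plan does name groups, so a rank sum comparison might be intended. Section 7.1.1 does refer to dose groups and control subjects, and it would be wrong to say that the plan has no groups at all. But those are groups for summaries, 7.2.7 does not call on them, and Step 2 shows that a between-group reading does not fit.

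A reader might also infer that the error inflates false positives, or that the trial will lose power for its clinical endpoints. Neither is supported. With uncorrelated or positively correlated measures the rejection rate under no change does not exceed the nominal level. Any loss of power depends on the misreading and on a correlation that the documents do not give.

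**Conclusion.** The point holds as a minor correction. Section 7.2.7 names the wrong non-parametric test for a within-subject change, and nothing elsewhere in the document puts it right.

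The consequence is small. The paired t-test option is valid. The measures are secondary, and Section 7.1.1 says that tests and intervals "are provided as an aid in interpreting study results and are not intended as claims". Descriptive statistics will be reported whatever the test. QMA has its own model in Section 7.2.6, and Section 3.3.1.1 already prefers it on the ground that it "reduces the number of subjects required to determine treatment effect in clinical trials when compared to other tested endpoints". No primary objective depends on 7.2.7.

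The contrast in p-values (0.0005 against 0.35, and 0.008 against 0.28) rests on invented data with a uniform decline, which is close to the extreme case for pairing. It shows the direction and mechanism of the error and does not estimate what will happen in this trial.

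**What to change.** In Section 7.2.7, replace the Wilcoxon rank sum test with the Wilcoxon signed-rank test. This is a change of wording that needs no new data, visits or subjects, and it removes the need to report use of the correct test as a deviation. The signed-rank test has slightly lower power only when repeat measures are uncorrelated or nearly so, which is not a practical drawback for repeated measures in the same person.

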### **7.3. Determination of Sample Size**

Eligible subjects will be enrolled into one of 2 cohorts of 6 subjects each, to receive ManNAc at doses of 3,000 mg BID (n=6) or 6,000 mg BID (n=6). Given the rarity of disease and the intent of this study—determine pharmacokinetics, safety and efficacy using blood based and tissue biomarkers, 12 subjects should be suitable.

### **7.4. Interim Analysis**

Interim analyses are planned after each cohort has completed the pharmacokinetic phase, and after each cohort has undergone evaluation at days 182, 365, 548, 730 and 912 (6, 12, 18, 24, and 30 months).

## **7.5. Deviation from Original Analysis Plan**

Any deviation from the original statistical plan will be described in the final clinical study report.

## **8. POTENTIAL BENEFITS**

### **8.1. Direct benefits to participants**

The benefits of ManNAc are unknown. There may be no direct benefits to subjects participating in this study.

### **8.2. Collateral Benefit to Participants**

The results of clinical testing performed at NIH will provide data for each subject's medical record. The study team may serve as a resource for consultation with each subject's physician.

### **8.3. Benefits to Society**

This study will improve understanding of the safety and PK of ManNAc and its results will inform future trials to evaluate the efficacy of ManNAc in individuals with GNE myopathy.

## **9. LIKELIHOOD AND SERIOUSNESS OF HARMS AND MEANS TO MAXIMIZE SAFETY**

Efforts will be made to reduce physical and psychological stress by carefully explaining the study's procedures to the individual subjects.

Individual procedures and associated personal risks are briefly described below.

### **9.1. Therapeutic Interventions**

#### **9.1.1. Risks of ManNAc/ManNAc**

A single dose of ManNAc was safe and well tolerated as part of NIH study 12-HG-0207. The only drug-related adverse event in this study, loose stools shortly after receiving the 10,000 mg as a single dose of ManNAc, was likely caused by unabsorbed drug in the gastrointestinal tract. As part of this study, the maximum single dose to be given will be 6,000 mg, which was determined to be safe and well tolerated on NIH study 12-HG-0207 (See Appendix F).

One subject participating in study 15-HG-0068 had Grade 3 hypertriglyceridemia which was determined to be probably related to ManNAc. As higher triglycerides were also seen in toxicology studies (see Table 10), the intake ManNAc includes the risk of hypertriglyceridemia.

As mentioned in Section 3.6 and shown in Appendix L, effects on the gastrointestinal tract were the most prominent in the 90-day toxicology studies performed in rats and dogs, and included loose and discolored feces, mild liver enlargement and mucosal hypertrophy of the colon. There have been no serious adverse events through 24 months of follow-up visit for subjects taking ManNAc. Two subjects have withdrawn consent due to gastrointestinal tolerability issues. One subject had a dose reduction due to tolerability concerns associated with grades 1 and 2 flatulence and diarrhea, and the subject has had their symptoms reach a tolerable level at the reduced dose.

### **9.2. Diagnostic Interventions**

#### **9.2.1. Medical Evaluations**

There are no significant risks associated with the physical evaluations, or collection of vital signs. Multiple independent evaluations may be stressful.

#### **9.2.2. Serum Pregnancy Testing**

There are no risks involved with taking a serum pregnancy test. Subjects will be informed of a positive test. The subject will not be eligible to participate in the study if she is pregnant.

#### **9.2.3. ECG**

There are no significant risks associated with performing an ECG.

#### **9.2.4. Placement of a Peripheral Intravenous Line**

A peripheral intravenous line may be placed to allow for blood collection. Risks associated with a peripheral intravenous line include a small risk for infection, phlebitis, extravasation, infiltration, air embolism, hemorrhage, and formation of a bruise.

Because of the risk of insertion-site infection, the catheter needs to be removed within 72 hours.

### **9.2.5. Phlebotomy**

Multiple blood draws will be necessary during this study. Phlebotomy is a risk/discomfort of this study. An anesthetic cream such as EMLA may be used. Infection and bruising are possible at the site of the blood draw. The amount of blood to be drawn will not exceed the NIH CC blood draw limits of 550 mL over any 8-week period. Nursing staff will monitor blood-drawing volumes. If blood limits are an issue, testing will be prioritized by the investigators. Safety laboratory tests will take priority over investigational testing. If a subject is concurrently enrolled in another protocol, the total blood volume will not exceed the above limit.

### **9.2.6. Muscle Biopsy**

Muscle biopsies will be obtained when technically feasible. A separate NIH Clinical Center surgical consent will be used for this procedure. The open muscle biopsy will leave small scars on the skin; therefore subjects may have up to four scars, one per biopsy. The rare complications of local infection or bleeding will be guarded against by sterile procedures, and careful hemostasis. The risk of these events is minimized by having the procedure performed by a neurosurgeon or neurologist trained to perform muscle biopsies and under sterile conditions with adequate anesthesia.

To further decrease the risk of bleeding associated with muscle biopsy, anticoagulants, aspirin, clopidogrel and other medications that increase the risk for bleeding are stopped. Only subjects that can safely discontinue such medications, as determined by their treating physician, will be eligible for this study. Pre-surgery and post-surgery instructions, including care of the incision site, will be provided to the subject.

### **9.2.7. Muscle MRI**

Potential risks from MRI include injury from the MRI magnet if they have pacemakers or other implanted electrical devices, brain stimulators, dental implants, aneurysm clips (metal clips on the wall of a large artery), metallic prostheses (including metal pins and rods, heart valves, and cochlear implants), permanent eyeliner, implanted delivery pump, or shrapnel fragments. Welders and metal workers are also at risk for injury because of possible small metal fragments in their eyes. Subjects will be screened for these conditions prior to the test, and if they have any of these conditions, they will not have an MRI scan. In addition, all magnetic objects (for example, watches, coins, jewelry, and credit cards) must be removed before entering the MRI scan room. Women who are pregnant are excluded from the MRI. Therefore, all women of childbearing potential will have a pregnancy test performed, which must be negative, before proceeding. Subjects will be asked to complete an MRI screening form, and to sign a separate MRI consent for each MRI. There are no known long-term risks or consequences of MRI scans.

Holding still during the MRI scan and being placed in a relatively small space can be uncomfortable or create anxiety in some subjects, if desired a mild anxiolytic may be prescribed during the test. MRI evaluation does not involve any radioactivity.

### **9.2.8. Activity monitor**

The only reported adverse event associated with these devices is skin irritation when it is worn against the skin. If this occurs, the device can be moved to an alternate site that is not in direct contact with skin.

**9.3. Radiation**

Only medically indicated radiation exposure will be incurred.

**9.4. Sedation**

None.

**9.5. Psychological Harms**

The main psychological issue will be accepting the possibility that ManNAc administration is not beneficial.

**9.6. Risk to Family Relationships**

Subjects will have a known genetic condition. No further genetic testing will be performed for this study, therefore there is no risk to family relationships.

**9.7. Discrimination**

Subjects enrolled in this protocol already have the diagnosis of GNE myopathy, with its attendant risks of insurance and employment discrimination. To the fullest extent possible, the investigators will not disclose to third parties any information about the participants without their expressed consent.

## **10. PRIVACY AND CONFIDENTIALITY OF MEDICAL INFORMATION AND BIOLOGICAL SPECIMENS**

### **10.1. Participant Identifiers Attached to Data**

Clinical data will be collected using subjects' names in a "shadow" file, maintained in a locked cabinet. The Principal Investigator and designated Associate Investigators will hold keys to the locked cabinet. However, to maintain subject privacy, all CRFs, study drug accountability records, study reports, communications, and research blood samples will be identified by the assigned subject number and/or a barcode. The linking code, as well as all other data, will be maintained in records in the password-protected database CTDB.

### **10.2. Clinical/Demographic Information**

This will be part of the clinical data kept in the medical record and in password-protected database CTDB.

### **10.3. How might information make specific individuals identifiable?**

Subjects enrolled in this study are from all over the world. It is doubtful that any demographic information could identify an individual. Subjects will be notified that registration information, results, and other information about this study will be submitted to ClinicalTrials.gov, a publicly available trial registry database; however, protected health information of individual subjects will not be used.

### **10.4. Access to the key for subject identification**

The code to subject identities, as well as other subject data, will be kept in the password-protected database CTDB. Access to the code will be restricted to the Principal Investigator, [name] and designated Associate Investigators.

### **10.5. Will pedigrees be published?**

Pedigrees are not essential for this drug trial.

### **10.6. Will results be provided to participants?**

All medically relevant data will be given directly to the subjects as they become available. In addition, the clinical research data of the individual subject, obtained in our CLIA-certified lab, will be provided to interested subjects.

